## **Statistical Design**

Primary clinical outcomes for this trial will consist of symptoms of depression and anxiety. We will compare scores on depression and anxiety (DASS) between the conditions using linear mixed-models. Linear mixed-models are robust to missing data as they do not require complete case data (i.e., at every time point); thus, even participants with missing data at some assessments were included in the analysis and results are modeled on the basis of the available data. Missing data was imputed on any scale if less than 25% of the data was missing in which case the missing value was replaced by taking the mean of the non-missing items for that participant for that particular scale.

Models were a priori adjusted for age, gender, race/ethnicity as well as baseline levels of the dependent variables. For these models, we will include diagnostic status as baseline covariates in mixed-effects repeated measures model analysis using continuous measures (symptom change on DASS) as outcome variables. Mixed-models require at least 3 assessment time points and for dichotomous variables measured with telephone assessments at fewer time points we will be evaluated using descriptives, chi-square and t-tests. We will examine mediation using the Preacher and Hayes bootstrapping procedure. This procedure produces the bias-corrected and accelerated bootstrapped confidence intervals of the product of the direct pathways between condition and the mediator (a) and the mediator and the outcome (b) to estimate the indirect effect (ab).

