## **Objectives:**

This pilot effectiveness trial aims to determine the impact of the Crowd-Powered Platform on symptoms of depression and anxiety and evaluate whether the platform engages the putative targets of personal relevance and interpersonal relationship building, resulting in increased skills mastery and skills use. We will enroll 100 participants in a two-armed randomized controlled trial of the platform. Participants will be randomly assigned to receive either the crowd-powered platform (treatment) or a similar self-guided platform (control) that contains the didactic material (learning) but none of the crowd features. Participants will be recruited from Mental Health America (MHA)'s Screening-to-Supports platform, an online screening platform that conducts approximately 3000 screens each day. The MHA Screening-to-Supports platform includes screeners for depression (PHQ-9) and anxiety (GAD-7). Individuals who screen positive for depression or anxiety will receive brief online study advertisements. Study advertisements will be 1-2 sentences long, and include the following text: "Click here to take part in a 16 week paid trial and test a new online platform for depression and anxiety". Individuals who receive and click on these advertisements will have access to a REDCap form with screening questions regarding demographics, contact information, age, diagnostic status and English proficiency. Those who are eligible as determined by the web screener will be contacted by research personnel to schedule a 1 hour remote interview where they will 1) review the consent form with research staff and electronically sign via REDCap's e-consent form 2) complete a diagnostic assessment with modules of the SCID. Afterward, participants will be sent a REDCap link via email to complete baseline assessments and will receive login information for their assigned platform (e.g., treatment or control) via email. Participants will use their assigned platform for 8 weeks and will be instructed to use the platform at least 3 times per week. Participants will be sent weekly newsletters via Mailchimp.com, and text message reminders to complete surveys. These newsletters will include didactic information about the platform and platform content, reminders to engage with the platform, and reminders to complete study measures. Participants will receive trial assessments at baseline, week 4, and week 8 (post-treatment). Follow-up evaluations will occur at 16 weeks to evaluate maintenance of gains. In addition, a subset of participants will be asked to complete a one-hour evaluation of user experience at 16 weeks.

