## **Methods:**

Participants will be asked to interact with their assigned platform for 8 weeks, at least 3 times per week. Each platform interaction is estimated to take between 5-10 minutes, but participants may choose to engage on the platform for as long as they would like. Participants will be randomized into one of two conditions, where they may either interact with a version of this platform that includes content intended to teach you about mental health and skills, or a similar version that also includes peer support. Participants will be asked to complete an initial, one-time mental health assessment via Zoom call that will take approximately one hour. Participants will be sent weekly newsletters via Mailchimp.com. These newsletters will include didactic information about the platform and platform content, reminders to engage with the platform, and reminders to complete study measures. Email addresses will be used to send participants newsletters through Mailchimp.com. No additional identifying information will be shared with Mailchimp.com. Subjects may unsubscribe from Mailchimp

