newsletters at any time. When the study is complete, the contact list of subject emails will be deleted from Mailchimp. Participants will also complete a series of online surveys that will ask questions about their mental health, which will begin at the time of enrollment, and will be administered at 4 weeks, 8 weeks, and 16 weeks. Participants will receive text message reminders to complete surveys when they are received. Text message reminders will say the following: "Hello, this is a reminder from the Overcoming Thoughts Study to complete your [week 4, 8, 16] surveys. You must complete all surveys in order to receive the maximum payment. (These are very important to our research and we appreciate your time.) If you have any troubles, please contact us. Thank you!" At 16 weeks, an optional follow up remote interview will be conducted with a subset of participants to evaluate acceptability and usability. Researchers will conduct these follow-up interviews with a subset of participants using purposive sampling to identify those who did or not benefit balancing across the treatment and control arm, as well as those who had low and high usage. Benefit will be defined as those who received at least a 25% improvement from pre-treatment score on the DASS and a shift in category (e.g., moderate to mild). Interviewers will be blind to treatment condition as well as benefit and usage status. Each self-report assessment and remote interview will take approximately one hour. The total time required for each participant (including time spent on platform, 4 self-report assessments, and both possible remote interviews) is 10 hours. All remote interviews will be audio recorded for analysis and quality assurance. Researchers will gather usage data directly through the platform, such as number of log-ins and length of use per session.

"Crowduser" information refers to all user-generated responses submitted on the platform, which are subsequently visible to all other users accessing the site. The crowdsourced platform is publicly available on Mental Health America's website, therefore participants in the crowdsource condition may see content submitted by non-study participants. Information submitted by public users (non-participants) will not be gathered and included in the data report that UCI researchers receive. Only data gathered from the consented participants will be gathered for study purposes.

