**Feasibility metrics** will also be drawn from data collected through the ADAPT platform including the amount of time required to produce an acceptable response to a request, amount of time between notifications being sent to a user and their login to the platform. If professionals are required to generate some content, we will also estimate the cost of producing a response by tracking professional time and multiplying time by hourly pay rate. Adherence will be tracked as the number of days between a user's first and last login to the ADAPT platform as well as the number of unique days that the user visited the ADAPT platform. Users will be instructed to use the platform at least 3 times a week and we will also look at the number of weeks that users meet this expected level of use (0-8).

**Acceptability** will be assessed through quantitative ratings of the ADAPT platform at end of treatment. Additionally, we will conduct individual interviews with a subset of participants using purposive sampling to identify those who did or not benefit balancing across the treatment and control arm. Benefit will be defined as those who received at least a 25% improvement from pre-treatment score on the DASS and a shift in category (e.g., moderate to mild). Interviewers will be blind to treatment condition as well as benefit status.

**Target Outcomes** include measures of clinical symptoms, accountability, skill use and mastery, functioning, and use of the platform. We will use identical measures to the field trial. An online administered self-report assessment will measure depressive and anxiety symptoms using the DASS, accountability using the SAQ, skills use and mastery using the Frequency of Actions and Thoughts and Coping Self-Efficacy, and functioning using the PROMIS Ability to Participate in Social Roles and Activities Scale at baseline, week 4, week 8, and week 16. A telephone interview will consist of the SCID-5 for depression status and anxiety status at baseline. Use metrics include number of logins, number of times each task is completed (learning, requesting, responding), and time spent on the platform

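### Does the undefined diagnostic-status covariate leave the primary DASS model open to materially different answers?

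*SAP*

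**What the plan says.** The SAP (Statistical Design) compares DASS depression and anxiety scores between arms with linear mixed models. On covariates it states that "Models were a priori adjusted for age, gender, race/ethnicity as well as baseline levels of the dependent variables", and then that "we will include diagnostic status as baseline covariates in mixed-effects repeated measures model analysis". It does not name an instrument, the disorders covered, the number of variables or their levels. The following sentence says mixed models need at least three assessments and that "for dichotomous variables measured with telephone assessments at fewer time points we will be evaluated using descriptives, chi-square and t-tests".

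The protocol describes two baseline items that could be meant:

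- Under Objectives, the web form contains "screening questions regarding demographics, contact information, age, diagnostic status and English proficiency". The same section adds that "Those who are eligible as determined by the web screener will be contacted by research personnel".
- Also under Objectives, enrolment includes a diagnostic assessment with SCID modules. In the Target Outcomes paragraph of Methods this becomes "A telephone interview will consist of the SCID-5 for depression status and anxiety status at baseline". Earlier in Methods participants are asked to "complete an initial, one-time mental health assessment via Zoom call".

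The DASS is collected online at baseline and at weeks 4, 8 and 16. The week-16 interview is optional, covers a subset, and concerns acceptability and usability.

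**The concern.** The covariate sits in the model for the primary clinical outcomes. The SAP's term for it matches the protocol's name for the web-screener question, while the protocol's diagnostic interview yields separate depression and anxiety statuses. One reading gives a single self-reported item and the other gives interviewer-rated indicators. If the choice is open, two analysts can report different estimates and p-values from the same plan, and someone who has seen the data could pick the more favourable one.

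The next SAP sentence does not settle the matter. It sets a rule for telephone-assessed dichotomous variables, yet the only such assessment described is the SCID-5 at baseline, so it has no outcome to test. The reason it gives is also wrong: mixed models do not require three time points.

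**Working it through.** **1. Which source is meant.** Setting the sections side by side favours the SCID-5.

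| Feature | Web-screener item | SCID-5 |
|---|---|---|
| When | before consent | enrolment interview, before login details are sent |
| Described as | one of several screening questions | the diagnostic assessment |
| Purpose shown | deciding whom to contact | recording depression and anxiety status at baseline |
| Number of variables | one item | two statuses, matching the SAP's plural covariates |
| Literal match to the SAP's term | yes | no |

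Only the last row favours the web item. If that item is an eligibility criterion, enrolled participants may hardly differ on it and it would be a poor covariate. This is inference, because the visible text does not list the criteria.

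**2. Whether a repeat SCID is planned.** The protocol states that "The total time required for each participant (including time spent on platform, 4 self-report assessments, and both possible remote interviews) is 10 hours". Its inputs (Methods) are about 1 h per survey and per interview, and 3 sessions a week of 5 to 10 minutes for 8 weeks.

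- Without a repeat: 4 × 1 h + 2 × 1 h + 24 × (5 to 10 min) = 6 h + 2 to 4 h = 8 to 10 h.
- With one more 1 h SCID: 9 to 11 h.

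The stated 10 h lies in both ranges, so the budget decides nothing. The wording does: the assessment is one-time and the SCID-5 is placed at baseline. The telephone rule can therefore only describe or compare baseline diagnoses.

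**3. Degrees of freedom.** The reference effect is the SAP's d = 0.50 with 50 per arm, alpha 0.05 and power 0.80 (Power section). Detectable d = (z_alpha + z_power) × sqrt(2/50):

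- One-sided: (1.645 + 0.842) × 0.20 = 0.497, which reproduces the stated 0.50.
- Two-sided: (1.960 + 0.842) × 0.20 = 0.560, which does not.

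The SAP does not state sidedness; that is a separate matter. For this point, two-sided power at d = 0.50 from the noncentral t is 0.697 with 98 df. It stays at 0.697 when the covariate uses 1, 2 or 3 of them.

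**4. Effect of the choice on the answer.** The simulation used 6000 trials per cell, 50 per arm and a baseline-adjusted ANCOVA on one post-baseline score, a simplification of the mixed model. The inputs are assumed, since the documents give none: each diagnosis shifts the outcome by 0.2, 0.4 or 0.6 units beyond the baseline score (outcome SD 1.02 to 1.16), the web item agrees with any SCID diagnosis in 70, 80 or 90% of participants, and about 60% are positive for each diagnosis. Web item against two SCID indicators, over the nine cells:

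- No treatment effect: each model rejects in about 5%; the better of the two rejects in 5.9 to 7.5%.
- True d = 0.50: the verdicts at p < 0.05 differ in 3.8 to 8.8% of trials.
- Mean absolute difference in the estimate: 0.026 to 0.060 SD (90th percentile 0.057 to 0.124 SD).

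The standard error of the difference between arms is sqrt(2/50) = 0.20 SD unadjusted. It is 0.20 × sqrt(1 − 0.36) = 0.16 SD if covariates explain an assumed 36% of the variance. The largest mean shift is thus 0.060/0.20 = 30% to 0.060/0.16 = 38% of one standard error.

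**5. The same question within the SCID reading.** A second simulation assumed a baseline slope of 0.6 and residual SD 0.8, with 3000 trials per cell and true d = 0.50:

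| Codings compared | Verdicts differ | Mean difference in estimate |
|---|---|---|
| two indicators vs any diagnosis | 2.9 to 5.9% | 0.02 to 0.04 SD |
| two indicators vs four categories | 0.9 to 1.5% | about 0.01 SD |

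**6. The three-time-point statement.** The DASS has four assessments, and three remain after baseline if baseline enters as a covariate. The mistaken requirement is met either way and excludes nothing.

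**The case for a change.** The strongest case for a change is that the gap is in the primary model, is real on the text, and would cost one SAP sentence to close. Choosing the SCID does not close it, since two indicators, a single any-diagnosis indicator and a four-level category all remain possible. A further simulation, with its own data-generating model over the same nine cells, agrees with the first on size: at least one of the two models rejects in 5.3 to 7.5% of null trials, verdicts differ in 3.9 to 9.3% at d = 0.50, and estimates differ by 0.026 to 0.058 SD. Allowing an any-diagnosis coding as a third choice raises the null figure to 5.6 to 7.9%.

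What stands is the ambiguity and the rough size of its effect on reproducibility. Three things limit it. The excess over 5% arises only if someone fits more than one model and reports the best; no single choice produces it. The larger figures come from the less plausible rival, with the web item assumed to vary freely among those enrolled. And because the candidates are fixed before platform access, choosing among them without regard to the results does not bias the comparison of arms.

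It could also be argued that, unless it supplies the covariate, the SCID has no stated use. That points toward the SCID reading, and the telephone sentence already gives the SCID a baseline use.

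**Conclusion.** No change to the plan is needed. The SAP omits a definition that an analyst would sensibly supply from the baseline SCID-5, and every reasonable coding gives a valid randomised comparison. Under the assumed inputs, the choice moves the estimate on average by 0.01 to 0.04 SD within the SCID reading, or 0.03 to 0.06 SD if the web item is used. That is well under one standard error, in a trial whose Power section describes a pilot for preliminary indications and says it is not fully powered on all outcomes. Writing the definition down would help reproducibility but would correct no error.

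The telephone sentence is a leftover that can apply only to baseline diagnoses, and deleting it would alter no DASS result. The telephone and Zoom labels for what appears to be the same baseline interview are a clerical mismatch. The conclusion rests on the SCID-5 being baseline-only, as the protocol's wording indicates, and on prognostic strength, agreement and prevalence lying within the simulated ranges. The documents give none of these three values.

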## **Scientific Background:**

Depression and anxiety are the most common mental health disorders in the United States with estimated 12-month prevalence rates of 18.1% and 9.5% respectively. These disorders commonly co-occur and it is estimated that over 70 million Americans each year will meet diagnostic criteria for either depression or anxiety. The human and economic burden of depression and anxiety are monumental. Depression alone is the leading cause of disability and represents the highest disease burden worldwide. Depression and anxiety have comparable impacts on quality of life and are associated with high levels of lost work productivity and increased medical costs. Efficacious treatments exist, yet many people fail to receive them. Estimates of service utilization indicate that among those meeting criteria for a mental disorder nearly 80% receive no treatment whatsoever. Barriers to treatment include costs, time, access, and stigma associated with mental health treatment. In response to these barriers, many researchers and healthcare systems have turned to technology-based treatment options, such as Internet websites and mobile apps, as alternatives to traditional face-to-face treatments. These interventions are referred to collectively as “behavioral intervention technologies” (or BITs) to distinguish them from other information and communication technologies that support healthcare more generally such as electronic medical records, clinical decision support programs, and telemedicine. As an alternative to traditional treatments, BITs allow users to access resources from anywhere in the world, at a time of their choosing. Various BITs for depression and anxiety have been evaluated with evidence supporting their efficacy. This includes Internet websites and mobile applications that draw from established evidence-based treatments such as cognitive-behavioral therapy (CBT), or transdiagnostic approaches. Despite their efficacy, one of the primary challenges that BITs face is sustained engagement. Open access BITs have particularly low rates of adherence with several studies finding only 1% of users complete all modules. Engagement tends to be better in clinical trials of BITs, with a systematic review finding completion rates ranged from 12-100% with a median of 56%. One characteristic that differentiated those trials with higher completion rates from those with lower completion rates was the use of human supported BITs. Completion rates in human supported BITs were found to be 80%, which compares favorably to face-to-face treatment. We think human support matters because it increases personal relevance of the techniques contained within the BIT and increases accountability. In traditional face-to-face CBT, the techniques factor refers to a therapist's fidelity to evidence-based practices while also acknowledging that adaptations must be made for each individual. In BIT treatments, fidelity to evidence-based principles can be very high, as it is pre-programmed. Most BITs, however, are not adapted for an individual and their needs. As such, we suggest that increasing the personal relevance within BIT treatments may increase skills use, mastery, and ultimately functioning. Personal relevance can be increased by including human supporters to clarify the use of the BIT and provide supplemental information to improve fit and use in a person's daily life. Human support also increases relational factors. In traditional face-to-face CBT, relational factors refer to the general qualities of the interaction between patient and therapist, and the therapist's ability to be attuned to their patients. In BIT treatments, relational factors have been most often described through the model of supportive accountability. In short, personally relevant therapeutic techniques and accountability drive skills use and mastery. Increased skills use and mastery results in improved functioning and clinical outcomes. Indeed, a robust literature links CBT skills use and mastery to outcome in therapy. Less research has evaluated what factors increase skills use, but BIT treatments provide a unique opportunity to explore this in detail through their ability to systematically collect data regarding skills use. This conceptual model helps illustrate why BITs that include human support have higher rates of engagement and greater efficacy. In order for BITs to reach their potential of offering scalable accessible interventions, novel strategies are needed to leverage non-professionals to support treatment engagement. This project explores enhancing BITs through crowd-powered processes. Crowdsourcing has been used in several successful technologies (e.g., reCAPTCHA, Foldit). At its core, crowdsourcing is a method for rapidly mobilizing large numbers of people to accomplish tasks on a larger scale. For effective

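### The mediation bootstrap has no stated way to keep participants who lack the mediator or outcome assessment; run on complete cases it loses precision and may bias the condition-to-mediator path

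*SAP*

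**What the plan says.** The SAP's Statistical Design section makes two provisions for missing data.

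- **Missed assessments.** In describing the linear mixed models for the DASS, it says that "even participants with missing data at some assessments were included in the analysis and results are modeled on the basis of the available data".
- **Missing items.** "Missing data was imputed on any scale if less than 25% of the data was missing", and the gap is "replaced by taking the mean of the non-missing items for that participant for that particular scale". This needs some answered items on the scale, so it cannot fill a survey that was not returned.

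Mediation is a separate analysis: "We will examine mediation using the Preacher and Hayes bootstrapping procedure". It is described as a bias-corrected and accelerated bootstrap interval for the product of path a (condition to mediator) and path b (mediator to outcome). The section does not state the analysis set, the mediator measure, the waves that supply mediator and outcome, or what happens when one of them is missing.

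The question is one of the trial's aims. The Protocol's Objectives say the trial will "evaluate whether the platform engages the putative targets of personal relevance and interpersonal relationship building". The SAP's Power section also lists target engagement among the purposes of the funding call. According to the Protocol's Methods, the DASS, accountability, skills, coping and functioning measures are all collected at baseline and weeks 4, 8 and 16. Logins, days of use, tasks completed and time on the platform are recorded by the platform.

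**The concern.** Path b needs a mediator value and an outcome value from the same person. If both paths are fitted by ordinary regressions on one data set, a common way to run this procedure, anyone lacking either value leaves the whole analysis. Suppose the mediator is taken at week 4 and the outcome later. A participant who returned week 4 but not the later DASS would then be lost from path a as well, although path a needs only condition and mediator.

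Membership of that subset is settled after randomisation, so randomisation no longer protects path a within it. The Protocol's own model makes informative retention plausible. Its Scientific Background holds that human support raises both accountability and engagement, accountability is a measured target, and only the treatment arm has the crowd features. If people with higher mediator values stay, and control loses more people, the retained controls are the more strongly selected group and path a shrinks.

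At stake is the target-engagement result. It would come from a smaller and differently selected sample than the DASS comparison.

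**Working it through.** **The plan's own figure.** The SAP gives none for mediation. Its only figure is a detectable d = .50 with 50 per arm, alpha .05 and power .80.
- One-sided: (1.645 + 0.842) × √(2/50) = .497, which reproduces it.
- Two-sided: (1.960 + 0.842) × √(2/50) = .560, which does not.

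This does not decide the present point, but 50 per arm is the starting size used below.

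**Precision.** Two-sided power for a difference of .50 SD, by assumed loss in each arm:

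| Loss | n per arm | Power |
|---|---|---|
| 0% | 50 | 70.5% |
| 10% | 45 | 66.0% |
| 20% | 40 | 60.9% |
| 30% | 35 | 55.2% |
| 40% | 30 | 49.1% |

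**Bias in path a.** All inputs are assumptions except where noted.
- The mediator M has SD 1 within arm. True a = .50 and b = .40, so the true indirect effect is .20.
- Logit of retention = c + s × M, with s = .5 or 1.0 in both arms and c set in each arm to give retention p.
- The 80% and 56% are the Protocol's literature figures for intervention completion (human-supported programmes, and the median across trials). Using them as survey retention is an assumption. The 85%/80% and 85%/75% pairs are milder assumed gaps.

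Among those retained, the mean of M rises by δ(p, s) = E[(M − μ) × P(retained | M)] / p, where μ is the arm mean. Numerical integration gives:

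| Retention p | δ, s = .5 | δ, s = 1.0 |
|---|---|---|
| 85% | .073 | .133 |
| 80% | .096 | .173 |
| 75% | .120 | .213 |
| 68% | .152 | .269 |
| 56% | .208 | .364 |

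Complete-case a = .50 + δ(treatment) − δ(control):

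| Retention, treatment/control | s = .5 | s = 1.0 |
|---|---|---|
| 85%/80% | .50 + .073 − .096 = .477 | .50 + .133 − .173 = .460 |
| 85%/75% | .50 + .073 − .120 = .453 | .50 + .133 − .213 = .420 |
| 80%/56% | .50 + .096 − .208 = .388 | .50 + .173 − .364 = .309 |
| 68%/68% | .500 | .500 |

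Large simulations of the same set-up agree to about .01 (.47, .43 and .32 in the steep-slope column for the three unequal pairs).

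Selection here is on M and arm, and path b is estimated given both, so b is unaffected. The proportional loss in the indirect effect is therefore (.50 − a)/.50: 5–8%, 9–16% and 22–38% for the three unequal pairs. If true a is 0, the same differences give −.02 to −.04, −.05 to −.08 and −.11 to −.19 SD.

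**Power for the indirect effect.** Simulated trials of 100 people with a percentile bootstrap:
- At 80%/56%, power is 23–35% on complete cases, against 57–63% if path a uses everyone and all participants supplied the mediator.
- At 68%/68%, it is about 47% against about 60%.

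**Other loss patterns.** A separate simulation adjusted path a for the baseline mediator and set true a = 0 with about 30% loss.
- No bias: loss that was completely random, depended on arm only, depended on the adjusted baseline value, or depended on the mediator identically in both arms.
- Loss depending on the outcome in control only: −.07 SD (type I error 6.4%).
- Loss depending on the mediator in control only: −.18 SD (12.6%).
- Loss depending on the mediator in opposite directions by arm: +.35 SD (39%).

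**The case against.** The strongest reply is that this is silence, not a stated defect. The SAP names no software and no complete-case set, and a full-information or multiply imputed bootstrap of the product would fit its wording. That is right. A reader might infer that anyone who misses an assessment is dropped and that path a is therefore no longer a randomised comparison. The documents do not support that. Only the waves supplying mediator or outcome matter, and they are not named: someone missing week 16 alone stays in a week 4/week 8 model. Path a can also be estimated in everyone with a mediator value.

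The discarded-mediator argument needs a lagged design. The measures sit in one survey at each wave, so if mediator and outcome come from the same wave, a missed survey loses both and no same-wave mediator value is thrown away.

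The largest bias rests on a 24-point retention gap borrowed from intervention completion. No document predicts that gap for surveys, and the reminders tie completing all surveys to maximum payment. The 57–63% power is a best case. In a further run with slope .5, power was 35% on complete cases, 51% when half of the non-returners had a mediator value, and 68% when all had. The runs used a percentile bootstrap, whereas the SAP specifies the bias-corrected and accelerated form.

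Mediation is also not the primary clinical outcome, and the SAP says the pilot is not fully powered on all outcomes.

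All of this limits the size and certainty of the problem. It does not supply a rule for keeping participants in an analysis that serves a stated aim.

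**Conclusion.** The point holds in conditional form. As written, the SAP gives the mediation bootstrap no means of retaining participants who lack the assessment supplying mediator or outcome. If it is run on complete cases, loss of precision is certain once anyone is missing. Bias in path a is a risk that depends on the pattern of loss.

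Under the assumptions above, the bias is small with a 5-point retention gap (a of about .48 to .46 instead of .50), moderate with 10 points (.45 to .42) and substantial with 24 points (.39 to .31). It is nil at equal retention with the same slope in both arms. Equal retention alone is not a safeguard, because slopes that differ by arm can bias path a even then. With no survey dropout rate in the documents, no one of these cases can be called the expected one.

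The change should be made because it is cheap and target engagement is a stated aim. It does not call the DASS mixed-model comparison into question.

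**What to change.** Amend the mediation text in the SAP's Statistical Design section to:

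1. Name the mediator and outcome for each mediation model and the wave of each, with the mediator measured before the outcome.
2. Estimate the indirect effect on all randomised participants, using either a full-information maximum likelihood path model with bootstrap or multiple imputation within the bootstrap.
3. Include arm, all DASS and mediator waves, the baseline covariates and the platform use logs (logins, days used). The logs exist whether or not a survey is returned.
4. Report the complete-case result as a sensitivity analysis, with the number contributing to each path by arm.

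The cost is SAP wording, modest extra programming and more computing. The method relies on the observed waves and logs to explain why assessments are missing. If a mediator survey is missed for reasons tied to the unseen mediator value, some bias can remain.
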